4.2.5 Clinical study TCH-004 (NCT04089761)

A multicenter study of the Nerivio device in adolescent patients (age 12-17, inclusive) with migraine was performed to assess the performance of Nerivio in the adolescent migraine population. This study has also been previously presented to FDA in the 510k pre-market notification (K203181) and is summarized below for completeness.

Study design and procedures

This study was a prospective, open-label, single arm, multicenter study conducted across 12 clinical US sites. Participants entered a 4-week “Run-in” phase in which they had to report their migraine attacks and continue with their usual treatment care. Participants who reported at least 3 qualifying migraine headaches with pain data at baseline and 2 hours post-treatment were eligible to continue to the “Treatment” phase. During the “Treatment” phase, participants were asked to treat their migraine attacks at home for 8 weeks with their optimal stimulation intensity, as soon as possible after migraine headache began and always within one hour of attack onset. Participants were instructed to avoid taking rescue medications within the first two hours post-treatment. Pain scores (none, mild, moderate, or severe), absence/presence of migraine associated symptoms including nausea/vomiting, photophobia and phonophobia, and functional disability were recorded at baseline, 2- and 24-hours post-treatment in electronic diary application included in the Nerivio mobile application that was installed on the participants’ smartphones.

Participants who finished the “Treatment” phase were offered to continue to an 8-week follow-up phase in which they could incorporate the device into their usual care. Following the 8 weeks of “Follow up” phase, participants fill out their end of study questionnaire and completed the study.

Results

Run-in phase

A total of 267 qualifying migraine attacks were reported during the run-in phase by 54 of the 60 enrolled patients (6 patients did not report any migraines during the run-in phase), with an average of 4.9 migraine attacks per participant

Treatment phase

A total of 159 qualifying migraine headaches were treated with Nerivio for which pain data was recorded at baseline and at 2 hours post-treatment (average of 3.5 treatments per participant). Pain severity of treated migraine headaches was mostly

	QMS document Nerivio TCH-008 Clinical Study Protocol	Doc ID: TEC0250 Revision #: 3.0 Page: 29 of 58
---	--	--

moderate (48.4% [77/159]). 57/159 (35.8%) of the treated migraine headaches were severe and 25/159 (15.7%) of the treated migraine headaches were mild

Pain relief and pain-free at 2 hours were achieved by 71.8% (28/39) and 35.9% (14/39) participants, respectively. Pain relief was sustained for 24 hours in 90.9% (20/22) of the participants, and pain freedom was sustained for 24 hours in 90.9% (10/11) of the participants. Nausea, photophobia, and phonophobia disappeared at 2 hours in 54.5% (12/22), 41.9% (13/31), and 40.0% (10/25) participants, respectively. Furthermore, 69.7% (23/33) participants experienced improvement in functional ability at 2 hours and 69.0% (20/29) participants experienced improvement in functional ability at 24 hours.

a consistency analyses was conducted across all treated attacks (excluding the training treatment). This analysis demonstrated that 66.7% (26/39) of the participants experienced pain relief in at least 50% of their treated attacks, and 33.3% (13/39) of the participants experienced pain-free in at least 50% of their treated attacks.

Safety analyses were performed on all 45 participants who used the device at least once. 10 participants (22.2%) reported at least one adverse event. There was one device-related adverse event reported (2.2%) in which a temporary feeling of pain in the arm was felt. This adverse event was mild and resolved after the treatment without requiring medication or any other intervention. The other adverse events which were deemed unrelated to the device.

The findings of the study show that Nerivio is effective for the acute treatment of migraine in the adolescent population. The results of the study show that Nerivio is safe to use and is well-tolerated by adolescence migraineurs. The incidence of device-related adverse events was low with no device-related serious adverse events.

4.3. Clinical investigation risks and benefits

4.3.1. Anticipated benefits to participants

The clinical studies conducted in adults demonstrated that REN provides superior clinically meaningful relief of migraine pain and MBS compared to sham-device with a favorable safety profile, offering a safe and effective non-pharmacological alternative for acute migraine treatment. It is anticipated that the use for preventive treatment will be experienced with a similar safety profile.

4.3.2. Risks and adverse effects

The results of the pivotal study demonstrate a favorable safety profile of the device. In this study, adverse event incidence was low; mainly reports of sensation of warmth, redness and numbness of the arm/hand. All device-related adverse events were mild, resolved within 24 hours and did not require medical treatment. There were no device-related serious adverse events, no unanticipated adverse device effects and none of

	QMS document Nerivio TCH-008 Clinical Study Protocol	Doc ID: TEC0250 Revision #: 3.0 Page: 30 of 58
--	--	--

the participants withdrew from the study due to adverse events. The safety profile of the device is favorable compared to triptans [26] and to new pharmacological agents, such as centrally acting serotonin (5-HT1F) agonists that lack cardiac vasoconstrictive activity [27]. Furthermore, the device has comparable or superior efficacy to commercially available neuromodulation devices [21,24].

4.3.3. Risk-benefit balance

The data collected in the randomized controlled clinical study in adults demonstrated that acute treatment of migraine with Nerivio results in most important clinical benefits with a very low risk to the patient. Invoking conditioned pain modulation using peripheral neuromodulation that induces a general analgesic effect resulted in favorable 2-hour pain relief and pain-free responses which are comparable with pharmacological acute migraine treatments such as triptans with a more favorable safety profile. Overall, the benefit-risk balance of Nerivio is favorable, and was not changed when frequency of use was increased significantly for over 15 times per month by chronic migraine patients. Using the device for a preventive treatment is not expected to pose any new risks, since the device will be used every other day, resulting in ~15 days per month. The overall risk posed by the device is minimal. The device may offer an alternative non-pharmacological treatment that includes both acute and preventive treatments, without needing a variety of pharmacological agents that increases the risk of medication overuse, improve treatment adherence and considerably improve the health and quality of life of patients with migraine.

5. OBJECTIVES & HYPOTHESES

5.1. Study objectives

The objective of this study is to evaluate the safety and efficacy of Nerivio for the preventive treatment of migraine. The goal of this study is to demonstrate a reduction in the number of migraine headache days per month while maintaining a favorable safety profile.

5.2. Study hypothesis

The hypothesis of this study is that treating with Nerivio every other day will reduce monthly migraine headache days, while maintaining a favorable safety profile. This will be demonstrated by a significant difference between the active and the sham groups in the mean change in monthly migraine days from the baseline phase to the last 4 weeks of treatment phase.

	QMS document Nerivio TCH-008 Clinical Study Protocol	Doc ID: TEC0250 Revision #: 3.0 Page: 31 of 58
---	--	--

6. STUDY DESIGN

6.1. Participants

This study will be conducted on up to 375 participants.

6.1.1. Inclusion criteria

- Age 18-75 years old
- Must have at least a 6-month history of headaches that meet the ICHD-3 diagnostic criteria for migraine with or without aura, either chronic or non-chronic migraine.
- History of 6 to 24 headache days per 28-day period for each of the 3 months preceding study enrolment (based on patient report).
- Subjects on prophylactic migraine treatment are permitted to remain on 1 medication with possible migraine-prophylactic effects if the dose has been stable for at least 2 months prior to the screening visit, and the dose is not expected to change during the course of the study.
- Have personal access to a smartphone (24/7).
- Must be able and willing to comply with the protocol.
- Must be able and willing to provide informed consent.

6.1.2. Exclusion criteria

- An active implanted electrical and/or neurostimulator device (e.g. cardiac pacemaker, cochlear implant).
- Uncontrolled epilepsy.
- History of use of opioids or barbiturates on more than 4 days per month in the last 6 months.
- Current participation in any other interventional clinical study.
- Participants without basic cognitive and motor skills required for operating a smartphone.
- Pregnant or breastfeeding.
- Other significant pain, medical or psychological problems that in the opinion of the investigator may confound the study assessments.
- Prior experience with the Nerivio device.

6.1.3. Withdrawal / Discontinuation

Participants may withdraw consent at any time and do not have to provide an explanation.

Participant may be withdrawn from the study by the PI or sponsor due to one or more of the following reasons:

- Participant is lost to follow-up
- Refusal of the participant to continue treatment and/or follow-up observations

	QMS document Nerivio TCH-008 Clinical Study Protocol	Doc ID: TEC0250 Revision #: 3.0 Page: 32 of 58
---	--	--

- Serious adverse event
- Participants encountering difficulties with the investigational product (IP) (e.g. cannot tolerate the treatment, unable to operate the application)
- Significant protocol deviation/violation or noncompliance, either by the patient or the investigator
- Decision made by the investigator that termination is in the patient's best medical interest
- Device malfunction
- Other ethical or clinical considerations upon investigator discretion

6.2. Stimulation program

Nerivio device - The device produces a proprietary electrical signal comprising a modulated symmetrical biphasic square pulse with a modulated frequency of 100-120Hz, pulse width of 400 μ s, and up to 40mA output current (adjusted by the participant). The duration of the treatment is 45 minutes.

Sham device- The device produces electrical pulses of similar width and intensity, but much lower frequency compared to the active device. It produces an electrical signal comprising a modulated symmetrical biphasic and rectangular pulse with a modulated frequency of 0.11-0.2Hz, pulse width of 300-1700 μ s, and up to 34mA output current (adjusted by the participant). The duration of the treatment is 45 minutes. This sham program produces pulses that are perceivable by the user, thus maintaining the blinding, but on the other hand do not intend to activate the CPM as a pain relief mechanism.

6.3. Procedures

This study includes up to four visits. Each visit can be performed either on-site or remotely, using a teleconference software. The means of remote visits will be documented in the site binder prior to site initiation. Each visit will have a time window of 10 days after the perspective visit date to complete the study visit.

Pre visit evaluation-

A candidate patient for the study will be asked by the clinic to complete an online questionnaire that will assess the patient compliance to participate in the study. A summary of the questionnaire will be sent to the clinic for review. The PI will use the data from the questionnaire to evaluate the patient ability to comply with the study requirements.

First visit –

The first visit will include screening, enrollment and training on the application.

Enrollment: The screening process will include an eligibility assessment and a urine pregnancy test. Following successful screening, the site staff will provide the participants

	QMS document Nerivio TCH-008 Clinical Study Protocol	Doc ID: TEC0250 Revision #: 3.0 Page: 33 of 58
---	--	--

with study related information, perform an enrollment interview and receive an informed consent from the participants. During this visit, participants will complete baseline questionnaires that includes information on frequency of migraine attacks, typical associated symptoms, use of preventive and acute treatments, and the effect that their migraine attacks have on their daily routine and quality of life (HIT-6 and MSQ questionnaires).

Application training: Eligible participants who enroll to the study will be trained to use the application that will be installed on their own smartphones. The participants will be instructed to complete a daily diary that included information on, headache with time of onset, migraine symptoms, and medication use. The site personnel will be required to document the training session in the CRF.

Baseline phase:

After the enrollment visit, participants will undergo a 4-week baseline phase aimed to collect headache days, medication use, migraine symptoms, and further assess eligibility. Participants will use the app daily to record headache with time of onset, migraine symptoms and medication use. To ensure compliance, the app will send daily reminders/notifications in a pre-specified time in the evening chosen by the participant, but the questionnaire will be available throughout the day. The daily reports will be transferred by the application to the electronic data capture (EDC) system, where they will be collected and registered.

Qualification to enter into the treatment phase: Participants who complete the diary in at least 22 out of the 28 days during the baseline phase (80%), have between 6 to 24 headache days during the 28-day baseline period, at least 4 of their headache days during the baseline phase fulfill the ICHD-3 criteria for migraine (migraine without aura [code 1.1; C and D], or with aura [code 1.2; B and C], or probable migraine, or headaches requiring the use of migraine-specific medications such as triptans, gepants or ergot derivatives) will continue to the treatment phase. Participants who fail these criteria will be excluded from the study and considered screen failure.

Second visit-

Device training: Eligible participants who successfully complete the baseline phase will be randomized in a 1:1 ratio into one of the two groups: either active (treatment with Nerivio active device) or sham group (treatment with Nerivio sham device). During this visit, participants will receive general instructions on study procedures, device mode of operation and warnings/precautions. After the training, patients will be instructed to use the device at home every other day.

The site personnel will be required to document the training session in the CRF. If the visit is conducted remotely, the devices will be shipped/mailed to the participant beforehand, with clear instructions not to open the device before the training.

	QMS document Nerivio TCH-008 Clinical Study Protocol	Doc ID: TEC0250 Revision #: 3.0 Page: 34 of 58
---	--	--

Before the first device use, the participants will watch a short instructional video that includes how to pair the device, finding the optimal individual stimulation intensity level (perceptible but not painful, just below the pain threshold), and instruction to use the device every other day for 45 minutes and to complete a daily questionnaire.

Treatment phase:

During this 8-week phase, participants will be instructed to use the device every other day for 45 minutes. Participants will also be instructed to continue completing a daily diary with information on their headaches with time of onset, migraine symptoms and medication use, as performed in the baseline phase. Participants will be instructed to use the device with an intensity level that is perceptible but not painful. Adverse events will be reported throughout this phase of the study directly to the site staff and recorded in the CRF.

Participants can treat their migraine and headaches with their usual acute treatments. (Nerivio will not be used for acute treatment to avoid bias between the groups).

Blinding will be assessed at the end of the treatment phase when participants will be asked of their presumed group assignment (active, sham, do not know).

Third visit-

Transition to the follow-up phase (open label):

During the visit, participants will complete the following questionnaires:

1. Patient assessment of treatment group during the treatment phase
2. HIT questionnaire regarding weeks 9-12
3. MSQ regarding weeks 9-12

At the end of the 8-week treatment phase, participants from both arms (active and sham) may continue to an open-label follow-up phase in which they will receive an active Nerivio device to use during the follow-up phase.

Participants who meet the following conditions will be offered to enter the **pre-emptive follow-up phase**:

- Between 6 to 16 headache days during the baseline phase.
- Participants experience at least one prodromal symptom, within 24 hours prior to the onset of their migraine headache, in at least half of their migraine attacks during the baseline phase.
- Participants completed the daily questionnaires in at least 70% of the days during the treatment phase
- Treated every other day on at least 24 and no more than 32 days during the 56 days of the treatment phase.

theranica	QMS document Nerivio TCH-008 Clinical Study Protocol	Doc ID: TEC0250 Revision #: 3.0 Page: 35 of 58
------------------	--	--

All other patients will be offered to receive an active device and continue in a safety follow-up, using Nerivio for preventive treatment of migraine, as instructed in the treatment phase.

Follow-up phase (open label):

Participants who continue into this 4-week period of follow-up phase, will receive an active device. Those who do not meet the requirements (see above) will use Nerivio for preventive treatment of migraine, as performed during the treatment phase. Participants will continue to complete a daily diary and use the device every other day for 45 minutes.

Participants who meet the requirements (see above) will receive the device for preemptive treatment of migraine. Participants will be instructed to use Nerivio within 60 minutes of prodrome symptoms onset, prior to the start of a headache, for a 45-minute treatment. The participants will be instructed to complete questionnaires regarding their headache, prodrome symptoms, and medication use at baseline (start of treatment), 2 hours post-treatment and 24 hours post-treatment. In addition, participants will be instructed to continue to complete the daily diary as in the baseline and treatment phases.

Participants will be permitted to take their usual care medications during this phase, except for the timepoint between starting a device treatment until 2 hours after treatment start.

Fourth (final) visit – End of study:

During the final visit, participants may be asked to fill additional questionnaires on their migraine and their experience with the device. In addition, all study devices will be returned to the clinic, either in person or by mail/shipment.

Study design is summarized in Figure 4 below.

[figure not shown]

Figure 4: Study design

6.3.1. Study duration

The duration of the study for each participant is expected to be up to 16 weeks.

6.4. Study endpoints

6.4.1. Primary efficacy endpoint

Difference between treatment groups in the mean change in number of migraine headache days per month comparing the 4-week baseline phase (weeks 1 through 4) with the last 28 days of the treatment phase (weeks 9 through 12).

A migraine headache day is defined as a calendar day with headache that is accompanied by at least one of the following symptoms: aura, photophobia, phonophobia, nausea and/or vomiting; or a calendar day with a headache that is successfully treated with a migraine-specific acute medication.

6.4.2. Secondary efficacy endpoints

1. Difference between treatment groups in the mean change in number of moderate/severe headache days per month comparing the 4-week baseline

	QMS document Nerivio TCH-008 Clinical Study Protocol	Doc ID: TEC0250 Revision #: 3.0 Page: 37 of 58
---	--	--

phase (weeks 1 through 4) with the last 28 days of the treatment phase (weeks 9 through 12).

A moderate/severe headache day is defined as a calendar day with moderate or severe headache.

2. Difference between treatment groups in the mean change in the number of headache days per month from the 4-week baseline phase (weeks 1 through 4) to the last 4 weeks of the treatment phase (weeks 9 through 12). A headache day is defined as a calendar day with headache (at any severity).
3. Difference between treatment groups in the percentage of patients achieving at least 50% reduction from baseline in the mean number of headache days (all severities) per month in the last 4 weeks of the treatment phase (weeks 9 through 12).
4. Difference between treatment groups in the mean change from baseline in the HIT-6 total score in the last 4 weeks of the treatment phase (weeks 9 through 12).
5. Difference between treatment groups in the mean change from baseline in the MSQ role function in the last 4 weeks of the treatment phase (weeks 9 through 12).

6.4.3. Exploratory efficacy endpoints

1. Difference between treatment groups in the reduction in the mean number of acute headache/migraine medication days per month in the last 4 weeks of the treatment phase (weeks 9 through 12) compared to Baseline (weeks 1 through 4).

An acute headache/migraine medication day is a calendar day on which the patient consumes at least one dose of any medication (OTC or prescribed) for acute treatment of headache or migraine.

[Endpoints below relate to the pre-emptive follow-up phase]

2. Percentage of patients who treat for the first treatment in the pre-emptive phase, during a prodrome, when they are pain free, and remain pain free during the following 2 hours after the treatment, without use of acute medication.
3. Percentage of patients who treat for the first treatment in the pre-emptive phase, during the prodrome, when they are pain free, and remain pain free during the following 24 hours after the treatment, without use of acute medication.
4. Percentage of patients who treat for the first treatment in the pre-emptive phase, during the prodrome, when they are pain free, and remain either pain free or

	QMS document Nerivio TCH-008 Clinical Study Protocol	Doc ID: TEC0250 Revision #: 3.0 Page: 38 of 58
---	--	--

with mild pain during the following 24 hours after the treatment without use of acute medication.

5. Mean change in the percentage of prodromes which were followed by a headache within 24 hours from baseline to the end of the pre-emptive follow-up phase.
6. Mean change in the average number of moderate/severe headache days per month in the pre-emptive phase compared to the 4-week baseline phase.

[Endpoint below relate to Health Economics analysis]

7. Differences between active and sham groups in reduction in the means of the following events from baseline (weeks 1-4) to second month of treatment (weeks 9-12):
 - a. Absenteeism – number of missed work/school days
 - b. Presenteeism – number of work/school days with moderate/severe functional disability
 - c. Healthcare provider appointments
 - d. ED/ER visits
 - e. Brain MRI/CT scans
8. Feasibility of a migraine prediction algorithm:
Analysis of the daily information provided by the participants for the purpose of developing a migraine prediction algorithm.

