7.2.3. Exploratory efficacy endpoints

Exploratory efficacy endpoints include:

1. Difference between treatment groups in the reduction of mean number of headache/migraine acute medication days per month in the last 4 weeks of the treatment phase (weeks 9 through 12). An acute headache/migraine medication day is a calendar day on which the patient consumes at least one dose of any medication (OTC or prescribed) for acute treatment of headache or migraine.
2. Percentage of patients who treat for the first treatment during a prodrome, when they are pain free, and remain pain free during the following 2 hours after the treatment, without use of acute medication.
3. Percentage of patients who treat for the first treatment in the pre-emptive phase during a prodrome, when they are pain free, and remain pain free during the following 24 hours after the treatment, without use of acute medication.
4. Percentage of patients who treat for the first treatment in the pre-emptive phase during a prodrome, when they are pain free, and remain either pain free or with mild pain during the following 24 hours after the treatment without use of acute medication.
5. Mean change in the percentage of prodromes which were followed by a headache within 24 hours from baseline to the end of the follow-up phase.
6. Mean change in the average number of moderate/severe headache days per month comparing the 4-week baseline phase with the follow-up phase.

	QMS document Nerivio TCH-008 Clinical Study Protocol	Doc ID: TEC0250 Revision #: 3.0 Page: 43 of 58
---	--	--

7. Difference between treatment groups in the reduction of the health economics metrics: absenteeism days, presenteeism days, ED/ER visits, physician appointments visits and CT/MRI scans – from weeks 1-4 to weeks 9-12.
8. Feasibility of a migraine prediction algorithm:
Analysis of the daily information provided by the participants for the development of a prediction algorithm for the purpose of predicting a migraine attack on the following day.

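### Exploratory endpoints 5 and 6 are uncontrolled changes from the device-free baseline, measured after 8 weeks of active or sham use, so they cannot be attributed to pre-emptive treatment

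*Combined protocol and SAP*

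**What the plan says.** After the 8-week double-blind phase, section 6.3 states that "participants from both arms (active and sham) may continue to an open-label follow-up phase". Everyone who continues receives an active device for weeks 13–16. Some enter the pre-emptive part and treat at prodrome. The others continue every-other-day prevention under safety follow-up.

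Entry to the pre-emptive part rests on four conditions in section 6.3:

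- Two use weeks 1–4: "Between 6 to 16 headache days during the baseline phase", and a prodrome before at least half of the migraine attacks.
- Two use the treatment phase: diary completion on at least 70% of days, and device use on 24 to 32 of the 56 days.

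Five exploratory endpoints in section 6.4.3 concern this phase. Endpoints 2–4 are first-treatment percentages, of the form "Percentage of patients who treat for the first treatment in the pre-emptive phase, during a prodrome, when they are pain free" followed by the outcome, with no baseline comparison. Endpoint 5 is "Mean change in the percentage of prodromes which were followed by a headache within 24 hours from baseline" to the end of the phase. Endpoint 6 is "Mean change in the average number of moderate/severe headache days per month in the pre-emptive phase compared to the 4-week baseline phase".

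In the same section, endpoint 1 does name the arms: "Difference between treatment groups in the reduction in the mean number of acute headache/migraine medication days per month". Endpoint 7 also names them. Endpoints 2–6 do not.

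Section 7.2.3 words endpoint 6 differently, as "comparing the 4-week baseline phase with the follow-up phase", without restricting it to pre-emptive users. It makes a similar change to endpoint 5.

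**The concern.** Endpoints 5 and 6 are meant to describe what pre-emptive use does. The comparator, weeks 1–4, comes before any device use, and the 8-week preventive intervention lies between the comparator and the measurement. Whatever is left of that intervention in weeks 13–16 is part of the measured change.

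The protocol's own rationale makes persistence plausible: section 3.6 hypothesises that frequent stimulation trains the pain-modulation mechanism. If that is right, former active participants may begin week 13 already improved. Former sham participants may still show a sham response. Without a by-arm summary or a weeks 9–12 reference, a reader of the results could not tell these contributions from an effect of treating at prodrome.

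What is at stake is how one exploratory question is interpreted. The randomised comparison at weeks 9–12 is not affected.

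**Working it through.** The plan gives no sample size, effect size or test for the pre-emptive endpoints, so there is no stated figure to reproduce. The check has three parts. Negative values mean fewer days.

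**1. What is compared with what (sections 6.4.3 and 7.2.3)**

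| Exploratory endpoint | Comparison | Arms named? |
|---|---|---|
| 1 and 7 | weeks 9–12 against weeks 1–4 | yes |
| 2–4 | none; percentage at first treatment | no |
| 5–6 | weeks 13–16 against weeks 1–4 | no |

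The baseline problem therefore concerns endpoints 5 and 6 only. Pooling of arms is implied by the contrast in wording; it is not written. Weeks 1–4 are device-free but not untreated, because section 6.1.1 allows one stable preventive medication.

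**2. How much could be carried in (endpoint 6)**

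Inputs:

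- Planned effect d = 2 days (section 7.4). This is for migraine headache days and is borrowed here for moderate/severe headache days.
- Share of former active entrants w = 0.5. This is assumed from 1:1 allocation.
- Fraction of the effect persisting into weeks 13–16, f. The documents do not give it, so it runs from 0 to 1.
- Lasting sham response s, common to both arms. The documents do not give it; 0 to 3 days is assumed.

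If pre-emptive use does nothing:

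- former active arm: change = −(s + d·f)
- former sham arm: change = −s
- pooled: change = −(s + w·d·f)

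With s = 0, the pooled change is 0.5 × 2 × 0 = 0, then 0.5 × 2 × 0.5 = 0.5, then 0.5 × 2 × 1 = 1.0 day of apparent reduction at f = 0, 0.5 and 1. With s = 3 and f = 1 it is 3 + 1.0 = 4.0 days. The range over these assumptions is 0 to 4.0 days.

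A weeks 9–12 reference behaves differently. If s persists, the former active change from weeks 9–12 is −(s + 2f) + (s + 2) = 2(1 − f). At f = 0.5 that is an apparent worsening of 1.0 day, and the former sham change is 0. Neither reference isolates pre-emptive use, but showing both by arm reveals what is being carried in.

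**3. Selection at entry, with no treatment effect (simulation, assumed distributions)**

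Endpoint 6: true mean of 8 to 14 headache days per 28 with between-person SD 5, extra month-to-month variation, and 60% of headache days moderate/severe. Change in moderate/severe days among those with 6–16 baseline headache days:

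| Assumed mean | Baseline rule only | Also 6–24 days in each of 3 prior months |
|---|---|---|
| 8 | −0.39 | +0.30 |
| 10 | −0.09 | +0.45 |
| 12 | +0.24 | +0.65 |
| 14 | +0.57 | +0.86 |

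The direction is not fixed. The lower bound of 6 pulls toward apparent improvement and the cap of 16 toward apparent worsening.

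Endpoint 5: each person has their own probability that an attack is preceded by a prodrome (three assumed distributions), plus an average of 1, 2 or 4 prodromes per 28 days with no headache after them. Selecting those with a prodrome before at least half of baseline attacks gave a fall in all nine scenarios. The smallest was 85.1% to 82.6% (2.5 points) and the largest 59.3% to 53.9% (5.4 points). Without selection the change was about 0. Here selection favours pre-emptive use.

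**The case against.** The strongest case against runs as follows. These endpoints are exploratory, open label and carry no hypothesis test. Weeks 1–4 are the only device-free diary period, so they are a defensible reference for pre-emptive use against usual care. Section 9.1 refers to a separately kept statistical analysis plan that might already split by arm. The Synopsis leaves the arms out even of the primary endpoint, so silence about arms is weak evidence of pooling. Pre-emptive entrants stop every-other-day use, so the preventive effect may fade and the carry-over may be zero.

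Most of this stands as a limit on size and wording. Exploratory status makes the consequence small. Pooling can only be called implied, and persistence may be nil. None of it supplies a control, a by-arm summary or a second reference in the plan as written.

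A reader might also infer that the repair is to make the weeks 9–12 change in former sham participants the main estimate. The documents do not support that. It compares a blinded sham with a device known to be active, on a new schedule, so expectation and loss of sham response are mixed in. Weeks 9–12 also lie inside the treatment phase used for the diary and device-use entry rules. It is a useful second view, not a clean one.

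**Conclusion.** The point holds for endpoints 5 and 6. As defined, each mixes any persisting preventive effect or sham response with the effect of treating at prodrome, and a change should not be attributed to pre-emptive use. Endpoints 2–4 are also uncontrolled but make no baseline comparison.

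For endpoint 6 the illustrative carry-in is 0 to 1.0 day in the pooled change, with any lasting sham response added. This rests on equal arms, on an effect borrowed from a different outcome, and on a persistence that the documents do not state. The selection artefact for endpoint 5 was a fall of 2.5 to 5.4 percentage points under assumed distributions.

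Two stronger readings are tempting and should not be adopted:

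- A reader might infer that endpoint 6 will show a spurious improvement of about 1 day. That is the full-persistence extreme; at zero persistence and no lasting sham response it is 0.
- A reader might infer that selection on baseline inflates both endpoints. For endpoint 6 the simulated bias ran from −0.39 to +0.86 days and was more often toward worsening.

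Separately, the wording in section 7.2.3 could bring participants who continue every-other-day prevention into endpoints 5 and 6. That conflicts with the restriction to the pre-emptive phase in section 6.4.3.

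**What to change.** - Report endpoints 2–6 by original randomised arm.
- For endpoint 6, report the change from weeks 9–12 beside the change from weeks 1–4. Moderate/severe headache days in weeks 9–12 are already derived for secondary endpoint 1, and the diary continues through follow-up. Do the same for endpoint 5 if prodromes are recorded in weeks 9–12; the description of the treatment-phase diary does not name them.
- Label all of these results descriptive, and state that the change is not attributed to pre-emptive use. Mention the baseline and adherence entry rules when the results are presented.
- Align endpoints 5 and 6 in section 7.2.3 with section 6.4.3, so that they cover participants in the pre-emptive phase only.

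No new data are needed for endpoint 6. The cost is a little more analysis and smaller groups, hence wider intervals, in each arm.
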